## PROTOCOL

### Background

#### 1. Provide the scientific background, rationale and relevance of this project.

##### INSTRUCTIONS

- This should include a referenced systematic evidenced-based review when possible.
- If this study involves qualitative research explain the major constructs of your study.
- Do not state in this section what you plan to do in this study. This information should be entered later under “What will be done in this protocol?”
- Do not include the bibliography in this section.
- For studies submitted under the Expedited review criteria, this section need not be more than a few paragraphs.
- For those studies where data will be analyzed collaboratively by multiple sites doing a similar study for which there is no common protocol (Collaborative Site Analysis Study) include a description of the common scientific goals/ procedures/data points.
- If this is a FIVE YEAR UPDATE make sure the information throughout the protocol includes the most current information.

Answer/Response: Postoperative bleeding in children undergoing cardiac surgery is a common complication that is associated with increased morbidity and mortality. While life saving during acute bleeding, the transfusion of red blood cells (RBC) and other blood-derived coagulation factors may be associated with serious postoperative complications such as infections, acute kidney injury, thromboembolic events, immunomodulation, volume overload (transfusion-associated cardiovascular overload, TACO) and lung injury (transfusion-related acute lung injury, TRALI) that can result in significant morbidity and mortality. Therefore, a significant effort is being invested in patient blood management strategies that will incorporate point-of-care-based transfusion algorithms and the use of novel coagulation concentrates in an attempt to reduce postoperative bleeding and need for allogeneic blood product transfusions after cardiac surgery.

Acquired fibrinogen deficiency is believed to be one of the key factors contributing to coagulopathy after cardiopulmonary bypass (CPB). Fibrinogen is the most abundant clotting factor in the human circulation and it plays a crucial role in hemostasis by promoting platelet aggregation and clot polymerization. However, it is also the first factor to be depleted during cardiac surgery, as there is no extra-vascular storage of fibrinogen. During cardiopulmonary bypass, fibrinogen levels may fall to 40-50% from baseline as a result of acute bleeding, hemodilution due to priming of the CPB circuit, consumption due to activation of the coagulation cascade and increased breakdown (hyperfibrinolysis). Thus, in post-CPB bleeding patients with low fibrinogen levels, replenishment of fibrinogen may be indicated to achieve adequate hemostasis.

Until recently, the only option for fibrinogen supplementation in the USA for patients with hypofibrinogenemia (either congenital or acquired) was the transfusion of cryoprecipitate. As such, the standard of care fibrinogen replenishment in bleeding

surgical patients with acquired fibrinogen deficiency is cryoprecipitate transfusion. Recently, however, the use of purified human fibrinogen concentrate (FC) has been approved in the USA and in Canada and its use in bleeding cardiac surgery patients has significantly increased and is recommended by transfusion guidelines in cardiac surgery patients. As such, UVA Medical Center has recently approved the use of fibrinogen concentrate as an alternative to cryoprecipitate in bleeding adult and pediatric surgical patients (including cardiac surgery patients).

FC is a lyophilized, nano-filtered and pathogen reduced and inactivated human fibrinogen concentrate with a constant content of 900-1300 mg/vial (final concentration 20g/L). While cryoprecipitate is still in use in North America, it is not available in Europe (except for the UK) due to safety concerns, as it does not undergo pathogen reduction and inactivation. FC has several important potential advantages over cryoprecipitate including: standardized fibrinogen content, higher purity, faster preparation without need for blood bank processing or cross-matching (which also eliminates the risk of human-related transfusion errors), improved safety via pathogen reduction, avoidance of transfusion related acute lung injury (TRALI) and significantly decreased volume of transfusion (which may be particularly important in children with congenital heart diseases as they may be intolerant to excessive volume overload). Yet, cryoprecipitate may be a better hemostatic agent as it also contains factors VIII and XIII, fibronectin, von Willebrand factor and platelet microparticles, all of which are important for normal hemostasis in bleeding patients. Hence it is not known whether FC will provide hemostatic efficacy similar to cryoprecipitate in bleeding pediatric cardiac surgery patients.

Initial studies evaluating the use of FC in cardiac surgery patients reported conflicting results. Surprisingly, several studies failed to report a benefit with the use of FC mainly due to enrollment of patients who did not have low fibrinogen levels. A recent large randomized controlled study in adult cardiac surgery patients, however, demonstrated non-inferiority of FC compared to cryoprecipitate in bleeding cardiac surgery adult patients with low fibrinogen levels (and as a matter of fact FC was found to be superior over cryoprecipitate in regard to several outcome measures). Hence it seems that FC may be a better alternative for fibrinogen supplementation in bleeding cardiac surgery patients compared to cryoprecipitate.

Despite the growing data about the potential advantages of the use of FC in adult cardiac surgery patients, it is not yet known, however, whether the use of FC in pediatric cardiac surgery patients may offer similar advantages. A recent prospective randomized study by Downey et al compared the use of FC to cryoprecipitate in pediatric patients undergoing cardiac surgery. Although there was no difference in postoperative bleeding between the study groups, children in the FC group received significantly less allogeneic blood products compared to patients who received cryoprecipitate. Some of the patients, however, also received prothrombin complex concentrate – a potent mixture of vitamin K-dependent clotting factors, which may complicate the interpretation of the results. Furthermore, the standard of care at the UVA Medical Center, as well as in other pediatric cardiac surgery institutions, is to prime the cardiopulmonary bypass pump only with RBCs without adding FFP (which is different than in the Downey paper). This results in a much more significant hemodilution that may lead to a higher risk of postoperative bleeding.

Taken together, there is a growing body of evidence supporting the use of fibrinogen concentrate as an alternative for cryoprecipitate in adult cardiac surgery patients, however, there is insufficient data in the literature to determine whether FC may be a comparable (or even a superior) alternative to cryoprecipitate for fibrinogen supplementation after pediatric cardiac surgery. Therefore, we propose a single-institution, prospective randomized pilot study to compare the use of FC (Fibryga, Octapharma USA, Hoboken, NJ, USA) to cryoprecipitate in pediatric cardiac surgery patients with postoperative bleeding and low fibrinogen levels. If FC is found to offer similar hemostatic efficacy as cryoprecipitate it may be a much better alternative for fibrinogen supplementation in bleeding pediatric cardiac surgery patients given its higher safety profile.

### Objectives/Hypothesis

#### INSTRUCTIONS:

If this study involves biomedical research clearly state the objectives and hypotheses and clearly define the primary and any secondary outcome measures. If this study involves qualitative research clearly state your research hypothesis or question.

This section should not include information already included in other sections such as background information or information from the procedures section.

Answer/Response: Our hypothesis is that fibrinogen concentrate will be as effective as cryoprecipitate in achieving adequate hemostasis after separation from CPB in pediatric cardiac surgery patients.

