**2. What are the statistical considerations for the protocol?**

The objectives section and the statistical section should correspond, and any objective for which analysis is unfeasible should be deleted. Also, the estimates and non-statistical assumptions of the statistical section should be supported by discussion in the background section.

The answer to this question should include:

- Study Design/Endpoints
- Recap of study objectives and endpoint definitions. An assessment of how study objectives will be assessed by identifying & defining which endpoints will be used to assess each component of the study objectives.
- The study design should include contingencies for early stopping, interim analyses, stratification factors (If applicable), and any characteristics to be incorporated in analyses.
- The power/precision of the study to address the major study endpoint(s), the assumptions involved in the determination of power/precision.

--If statistical hypothesis testing is included then specify the null and alternative hypotheses, the test statistic, and the type I and II error rates  
--If precision of an estimate, then provide a definition for precision  
--If other, then specify

Answer/Response: Baseline clinical and demographic characteristics, follow-up measures, and clinical outcomes will be compared on an intention-to-treat basis according to the randomized study group assignment. Continuous variables will be compared using the Student *t* test for normally distributed variables or the Mann-Whitney *U* test or Wilcoxon matched-pairs signed-rank test for non-normally distributed variables. Categorical variables will be compared using the Pearson  $\chi^2$  test or Fisher exact test as appropriate. We estimate that 30 patients would be needed (15 in each study arm) to determine that an exposure to 2 additional allogeneic blood products will be statistically significant (C.I. 95%) providing 80% power with a type I error probability  $\alpha = 0.05$  (including 20% dropouts/withdrawals from the study)

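### The hypothesis is that FC is as effective as cryoprecipitate, but the plan has only tests of difference and no margin or confidence-interval rule, so its analysis cannot support that claim

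*Combined protocol and SAP*

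**What the plan says.** Objectives/Hypothesis contains one hypothesis: "fibrinogen concentrate will be as effective as cryoprecipitate in achieving adequate hemostasis after separation from CPB in pediatric cardiac surgery patients". The last paragraph of the Background says what would follow from such a finding: "If FC is found to offer similar hemostatic efficacy as cryoprecipitate it may be a much better alternative for fibrinogen supplementation", on the ground of FC's better safety profile.

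Statistical Considerations, item 2, compares the arms by intention to treat. It uses the Student t, Mann-Whitney or Wilcoxon test for continuous variables and the Pearson chi-square or Fisher test for categorical ones. It sizes the trial at 30 patients, 15 per arm, "to determine that an exposure to 2 additional allogeneic blood products will be statistically significant", "providing 80% power with a type I error probability" of 0.05, "including 20% dropouts/withdrawals from the study". Item 3 calls the study a pilot and says that no power analysis was done. Item 4 names the primary outcome as any allogeneic transfusion in the 24 hours after the study product, with no test or success criterion.

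Non-inferiority appears once, in the Background, for a cited adult trial that "demonstrated non-inferiority of FC compared to cryoprecipitate in bleeding cardiac surgery adult patients with low fibrinogen levels". The plan gives no margin, equivalence bounds or confidence-interval decision rule for this trial.

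**The concern.** A claim that one treatment is as effective as another has to exclude a difference large enough to matter. A test of no difference does not do that: failing to reject may mean that the arms are alike, or only that the data are few and variable. Under this plan the hypothesised conclusion could come only from a non-significant result, and a smaller or noisier trial makes that result more likely.

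The error of most consequence is to call FC similar when haemostasis with it is worse. The Background itself gives a reason why this could happen: cryoprecipitate carries other haemostatic components besides fibrinogen.

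**Working it through.** **Inputs from the documents** (Statistical Considerations, item 2): difference 2 products, power 80%, alpha 0.05 (taken as two-sided, since sidedness is not stated), 30 patients in two equal arms, 20% dropout. Evaluable per arm: 15 × 0.8 = 12. **Not given:** the SD of the number of products, and any margin.

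**1. The plan's own figure.** Without an SD, 30 cannot be reproduced, so I solved for the SD. The normal formula is n per arm = 2 × (1.960 + 0.842)² × SD² / Δ², with (1.960 + 0.842)² = 7.849.
- At SD = 1.70 and Δ = 2: 2 × 7.849 × 2.89 / 4 = 11.3, so 12 per arm, 24 evaluable, and 24 / 0.8 = 30. This matches the plan.
- Power of exactly 80% with 12 per arm implies an SD of 1.75 (normal) or 1.67 (t test). With 15 evaluable per arm it implies 1.96 or 1.89.

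So 30 fits an ordinary two-sided superiority calculation with an unstated SD of about 1.7. I use 1.70 below because it takes the plan at its word.

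**2. How often a real deficit would be non-significant.** Two-sided t test at 5%, SD 1.70, noncentrality d / (SD × √(2/n)):

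| True excess with FC | 12 per arm | 15 per arm |
|---|---|---|
| 1 product | 72% | 66% |
| 1.5 products | 46% | 36% |
| 2 products | 21% | 13% |

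**3. What a non-significant result leaves open.** 95% CI half-width = t × SD × √(2/n).
- 12 per arm: 2.074 × 1.70 × 0.408 = 1.44 products.
- 15 per arm: 2.048 × 1.70 × 0.365 = 1.27 products.

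For example, an observed excess of 1 product with 12 per arm is non-significant, with a CI of 1 ± 1.44, or −0.44 to 2.44. That interval still contains the 2-product difference that the trial was sized to find.

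**4. The primary outcome as item 4 words it (yes/no).** No event rate is given, so I assume 50% to 90%. With 15 per arm, the CI half-width is 1.96 × √(2p(1−p)/15): 36 percentage points at 50% and 21 at 90%. Fisher power for a 20-point difference (50 v 70%, 60 v 80%, 70 v 90%) is 10% to 15%.

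**5. Whether 30 could serve a non-inferiority claim.** One-sided 2.5%, 80% power, true difference 0, same normal formula with the margin in place of Δ, and totals divided by 0.8 for dropout. The margins are illustrations only.
- SD 1.70: margin 2 gives 12 per arm, 30 in total; margin 1.5 gives 21 per arm, 53 in total; margin 1 gives 46 per arm, 115 in total.
- SD 2.5: margin 2 gives 25 per arm, 63 in total.
- Yes/no outcome, 20-point margin, before dropout: 198 in total at a 50% rate, 72 at 90%.

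**The case against.** The study calls itself a pilot in the Background and in item 3, and item 3 says that no power analysis was performed. A pilot does not need a confirmatory non-inferiority rule. The Background also asks whether FC might be superior, and tests of difference serve that question. Both points stand, and they are why estimation is the natural remedy. They do not remove the mismatch: item 2 claims 80% power, and the stated hypothesis is still one of similarity.

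A reader might go further than the documents allow in four ways.
- **That the sponsor will read p > 0.05 as similar efficacy.** No passage says so, and the Background sentence is conditional. What holds is that the plan offers no other route to that finding.
- **That the trial would usually miss even a 2-product deficit.** At an assumed SD of 3 it would, in 58% of trials with 15 per arm. But item 2 implies an SD of roughly 1.67 to 1.89 by the t test, where the miss rate is 20% by construction. A larger SD would be a separate sample-size question.
- **That 30 patients must be too few for non-inferiority.** Step 5 shows that 30 is enough at margin 2, SD 1.70 and no true difference.
- **That a margin can therefore be added with no extra patients.** This holds only under such conditions. At SD 1.89, margin 2 has 80% power with 15 evaluable per arm but 70% with 12, and tighter margins need far more.

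**Conclusion.** The point holds as a mismatch between hypothesis and analysis. The plan's sole hypothesis is similarity, and nothing in the plan can establish it. This follows from the text and needs no assumed figure.

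Its size does rest on assumptions. At an SD of 1.70 (back-solved, not stated), with a two-sided t test, an FC deficit of 1 product per child would go undetected in about two-thirds to nearly three-quarters of trials. On a yes/no outcome the interval would be wider still in practical terms: 21 to 36 points either side for assumed rates of 90% down to 50%.

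The defect is the missing margin and decision rule. Whether 30 patients is enough cannot be judged until the measure, the SD and any margin are stated.

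**What to change.** 1. First reconcile item 4 (any transfusion, which reads as yes/no) with item 2 (a number of products), so that there is one defined primary measure. Reconcile the power statement in item 2 with the statement in item 3 that none was made.
2. In keeping with the pilot status, restate the objective as estimation: report the FC minus cryoprecipitate difference on that measure with a two-sided 95% CI, and state that p > 0.05 will not be interpreted as similar efficacy.
3. If the sponsor wants to claim that FC is as effective, pre-state and justify a margin on that measure, make the claim only if the CI limit lies within it, and recalculate the sample size with a stated SD or event rate. The 2 products in item 2 is the difference the trial is sized to detect. The plan does not present it as an acceptable loss, so it is not a justified margin as it stands. Thirty patients may not give adequate power for a tighter margin, a larger SD or the yes/no outcome.

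Steps 1 and 2 cost protocol wording only; the downside is a weaker permitted conclusion. Step 3 may cost patients.

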### **4. What is your plan for primary variable analysis?**

Include primary outcome(s)/predictor variable(s), statistical methods/models/tests to be employed, or descriptive summaries as appropriate. If not applicable, please provide explanation.

Answer/Response:

Outcomes: the primary outcome of the study will be any allogeneic blood transfusion within the first 24 hours after administration of the FC or cryoprecipitate.

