### **5. What is your plan for secondary variable analysis?**

Include the following:  
--Secondary outcome(s)/predictor variables, statistical methods/models/tests to be employed, or descriptive summaries as appropriate. If not applicable, please provide explanation.  
--For phase III studies, the power/precision of the study to address the secondary objective(s).

Answer/Response: Secondary outcomes will include: administration of individual blood products (RBC, platelets, FFP, cryoprecipitate) over the initial postoperative 48 hours and up to 7 days after surgery, bleeding over the first postoperative 48 hours (intraoperatively = cell saver volume; postoperatively = chest drain/s output), the need for surgical re-exploration for hemostasis over the first postoperative 48 hours, the use of recombinant factor VIIa as rescue for refractory bleeding in the first 48 postoperative hours, length of ICU stay, hospital length of stay, thromboembolic complications over the first seven postoperative days and a 30-day composite of AKI, stroke, severe myocardial dysfunction or myocardial infarction, sepsis and

mortality (or until discharge whichever is earlier).

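### The hypothesis is about haemostasis but the primary outcome is transfusion, an indirect proxy that cannot by itself establish that fibrinogen concentrate is as effective

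*Combined protocol and SAP*

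**What the plan says.** Objectives/Hypothesis gives one hypothesis: "fibrinogen concentrate will be as effective as cryoprecipitate in achieving adequate hemostasis after separation from CPB". The closing paragraph of the Background makes the practical conclusion depend on the same idea: "If FC is found to offer similar hemostatic efficacy as cryoprecipitate". Neither place defines adequate haemostasis or gives a margin for similarity.

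Statistical Considerations, question 4, reads: "the primary outcome of the study will be any allogeneic blood transfusion within the first 24 hours after administration of the FC or cryoprecipitate". It does not restrict the reason for transfusion.

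The measures closest to haemostasis are in question 5, in one unranked list of secondary outcomes. One is blood loss, given as "bleeding over the first postoperative 48 hours (intraoperatively = cell saver volume; postoperatively = chest drain/s output". Two more cover the same period: a return to theatre, worded as "the need for surgical re-exploration for hemostasis over the first postoperative 48 hours", and rescue use of recombinant factor VIIa. Study Procedures adds ROTEM and fibrinogen measurements after the study treatment, but these are not listed as outcomes.

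The Background says of the earlier randomised paediatric trial of the two products: "Although there was no difference in postoperative bleeding between the study groups, children in the FC group received significantly less allogeneic blood products". It then notes that some patients received prothrombin complex concentrate, "which may complicate the interpretation of the results", and that the pump prime differed from local practice.

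**The concern.** A trial's primary outcome should be the quantity that its hypothesis is about. The form says so itself: the instructions to question 2 of Statistical Considerations ask for objectives and statistics to match. Here the hypothesis concerns stopping bleeding, and the primary outcome records whether blood products were given. The two are related but can separate, and the protocol cites a trial in which they appeared to.

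What is at stake is the meaning of the headline result. Similar transfusion in the two arms might be taken as similar haemostasis although part of that transfusion had nothing to do with bleeding. A difference in transfusion might arise without any difference in bleeding. The plan does not say how either pattern would be read. The question is a live one, because the Background itself raises the possibility that cryoprecipitate is the better haemostatic agent on account of its other clotting components.

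**Working it through.** **1. The plan's own figure.** Question 2 gives 30 infants (15 per arm) to detect a difference of 2 allogeneic products, with 80% power, alpha 0.05 and 20% dropout. No standard deviation (SD) is stated, so the figure cannot be reproduced; only the SD it implies can be found. With 15 × 0.8 = 12 evaluable per arm and a two-sided test, SD = 2 × √(12/2) / (1.960 + 0.842) = 1.75 products (1.67 with the t distribution). Question 3 says that no power analysis was done. Either way, the only sizing statement concerns a count of products. Nothing in the plan is sized for haemostasis.

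**2. The passages side by side.**

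| Place | Quantity |
|---|---|
| Objectives/Hypothesis | adequate haemostasis, as effective as the control |
| Background, conclusion | similar haemostatic efficacy |
| Question 2, sample size | number of allogeneic products |
| Question 4, primary outcome | any allogeneic transfusion, 24 h |
| Question 5, secondary outcomes | bleeding volume, re-exploration, rescue factor VIIa, among others |

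The claim is in the first two rows. The primary evidence is in the next two. The direct evidence is in the last, with no priority.

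**3. Why transfusion is only a proxy.**
- The outcome counts transfusion for any reason.
- Allocation is unblinded, and the documents state no trigger for transfusion.
- Question 5 lists cryoprecipitate as a blood product, and Study Procedures gives a second round of supplementation by randomised arm. Question 4 does not say whether that product counts. If it does, the same re-bleeding would score an event in the cryoprecipitate arm and not in the FC arm.

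**4. How far a proxy can dilute a difference (illustration; all inputs assumed).** Suppose the outcome is analysed as yes/no. Let h be the share needing a product for bleeding and q the share transfused for other reasons, independently. Then P(any) = 1 − (1 − q)(1 − h), so a difference in h shrinks by the factor (1 − q). With h = 60% v 30% and 15 per arm:

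| q | Any transfusion | Difference | Fisher exact power |
|---|---|---|---|
| 0 | 60% v 30% | 30 points | 23% |
| 0.5 | 80% v 65% | 15 points | 7% |
| 0.8 | 92% v 86% | 6 points | 1.5% |

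The documents give neither h nor q, and the dilution formula does not carry over to a count of products.

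**5. What the bleeding outcome could support (assumed CV).** The documents give no variability for bleeding. Take log-normal bleeding per kg with a coefficient of variation (CV) of 50% or 70%. The SD on the log scale is √ln(1 + CV²) = 0.472 or 0.631. For one-sided 0.025, 80% power, 15 per arm and a true ratio of 1, the excludable margin is 1.060 SD (t distribution; the same multiple as 2/1.887 from the product-count calculation at 15 per arm). The excludable ratios are exp(1.060 × 0.472) = 1.65 and exp(1.060 × 0.631) = 1.95. With 12 per arm the multiple is 2/1.671 = 1.197, giving 1.76 and 2.13.

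**The case against.** The strongest reply is that transfusion is far from irrelevant here. Infants enter because they have clinically significant bleeding and a low FIBTEM result, so products given in the next 24 hours are partly a consequence of whether bleeding was controlled. This stands. A reader might infer that the primary result cannot answer the question at all, and the documents do not support that. It bears on the question without settling it.

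Haemostasis is also not neglected: bleeding volume, re-exploration for haemostasis and rescue factor VIIa are all secondary outcomes. This stands too. What is missing is a definition of adequate haemostasis and any ranking among these measures.

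The evidence of divergence is thin. It is one trial, a finding of no difference is a failure to detect one, and the protocol itself warns about prothrombin complex concentrate. It shows that the pattern is plausible, which is all the point needs.

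A reader might also infer that less transfusion with the same bleeding would be reported as better haemostasis. No section says so. The hypothesis claims equal effectiveness, and the Background keeps bleeding and transfusion apart when describing the earlier trial.

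Finally, it is tempting to argue that bleeding volume has much more power than transfusion at this size. Power to detect a large difference is not power to support equal effectiveness, and step 5 shows how little 15 per arm can exclude. Bleeding is preferable because it matches the claim, not because it makes the trial conclusive.

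Pilot status does not remove the mismatch: a pilot still needs its outcome to match its question.

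**Conclusion.** The point holds in a limited form. The hypothesis and the intended conclusion are about haemostatic efficacy; the primary outcome is an indirect proxy not confined to transfusion for bleeding. The primary result alone therefore cannot establish that FC is as effective for haemostasis. This follows from the text and depends on no calculation.

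The sizes are illustrative. The dilution in step 4 rests on assumed h and q and a yes/no analysis. The 1.65- to 1.95-fold limit rests on an assumed CV of 50–70%, log-normal bleeding and full data on 15 per arm. The mismatch should be corrected, but it does not make the trial uninformative.

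**What to change.** 1. Reword Objectives/Hypothesis and the Background conclusion so that the primary comparison is of allogeneic transfusion exposure. State that this result does not by itself support a claim of equal haemostasis.
2. In question 4, say whether repeat doses of the study product count as transfusion events.
3. In question 5, name the existing bleeding outcome (cell saver volume plus chest-drain output, divided by weight) as the key secondary on which haemostasis is judged, over the 48-hour window already stated there.
4. Report it as a between-arm ratio or difference with a 95% confidence interval. Make no statement of equal effectiveness from a non-significant result, or without a margin fixed and justified in advance.

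**Cost.** Mostly wording. Weight and chest-drain output are already collected. Study Procedures records cell saver in units rather than volume, so a volume field is needed to match question 5. Because randomisation may occur in the operating room or the PICU, the 48-hour total will include some bleeding before the dose; this should be acknowledged, and the time of dosing recorded. A favourable transfusion result alone will no longer carry the headline claim, and the bleeding interval will be wide at this sample size.
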